#### INTENSITY OF AES

The intensity of the AE will be characterized as mild, moderate, or severe. Mild AEs are usually transient, require no special treatment, and do not interfere with the subject's daily activities. Moderate AEs traditionally introduce a low level of inconvenience or concern to the subject and may interfere with daily activities but are usually ameliorated by simple therapeutic measures. Severe AEs interrupt a subject's usual daily activity and typically require systemic drug therapy or other treatment. When the intensity of the AE changes over time, the maximum intensity will be recorded.

#### RELATIONSHIP TO OPTISON ADMINISTRATION

The relationship or association of the AE to the Optison administration will be characterized as "unlikely," "possible," or "probable." A relationship assessment will be performed by the investigator to determine if an AE is attributable to Optison and will be recorded on a data form. The investigator will refer to the Optison Package Insert for assistance in determining AE relationship.

An "unlikely" relationship indicates that there is little or no chance that Optison caused the reported AE; other conditions, including concurrent illnesses, progression or expression of the disease state, or a reaction to a concurrent medication, appear to explain the reported AE.

A "possible" relationship indicates that the association of the AE with Optison is unknown. However, the AE is not reasonably attributed to any other condition.

A "probable" relationship indicates that a reasonable temporal association exists between the AE and Optison administration and, based upon the investigator's clinical experience, the association of the event with the trial medication seems likely.

#### SERIOUS ADVERSE EVENTS

A "serious" AE (SAE) is defined as a significant clinical hazard, contraindication, or precaution that:  
Results in death

- Is life-threatening (In the opinion of the investigator, there is an immediate risk of death from the AE as it occurred. This does not include an AE that had it occurred in a more serious form may have caused death.)
- Results in a persistent or significant temporary disability/incapacity defined as a substantial disruption of a person's ability to conduct normal life functions
- Results in or prolongs an existing in-patient hospitalization (an overnight stay in the hospital, regardless of length) [Note: A hospitalization for an elective procedure or treatment which is not associated with an AE, hospitalization for a pre-existing condition which did not worsen, and hospitalization for reasons of convenience or observation, do not constitute an SAE.]
- Is a congenital anomaly/birth defect (in offspring of a subject taking the trial medication, regardless of time to diagnosis)
- Is an important medical event that may not result in death, be life-threatening, or require hospitalization but based upon the appropriate medical judgment, the event may jeopardize the subject and may require medical or surgical intervention to prevent one of the outcomes listed for the definition of a serious adverse experience.

All unexpected and serious adverse events are reported to the TJU IRB and to FDA if applicable. The investigator is required to submit all unexpected and serious adverse events to the TJU IRB and the data safety monitoring board within 48 hours. Fatal adverse events related to treatment which are unexpected must be reported within 24 hours to the TJU IRB and the DSMB through the CTSO.

The written report for any SAEs that occur during the study, whether or not related to the Optison administration will be submitted immediately (within 24 hours) to the TJU IRB.

The designated medical monitor will review all serious and unexpected adverse events associated with the protocol and provide an unbiased written report of the event within 10 calendar days of the initial report. At a minimum, the medical monitor will comment on the outcomes of the adverse event and relationship of the event to the Optison administration.

A copy of the SAE will be retained on file with the respective subject's data forms.

#### 6.7 End-of-Treatment and End-of-Trial Evaluations

Subjects will be free to discontinue trial participation at any time. The investigator will also discontinue any subject from the trial if, in the investigator's opinion, it is not safe for the subject to continue. The

date the subject is withdrawn from a treatment and/or from the trial and the reason for discontinuation will be recorded on the CRF.

Trial participation will be considered completed if the subject has met the following trial requirements:

- Has received two injections of Optison combined with 2D and 3D imaging of the area of interest

If a subject's participation in the trial is interrupted for any reason (e.g., because of an AE) and the subject has met the criteria described above for completing the trial, the subject's trial participation will be considered completed. If a subject's trial participation is interrupted for any reason by the subject's or investigator's choice and the subject has not met all of the criteria listed above, then the subject will be considered a discontinued subject.

Findings from this study will be submitted in abstract form to the annual meetings of the American Institute of Ultrasound in Medicine, the Radiological Society of North American, and the American Urological Association. A manuscript detailing study findings will also be submitted to either a Radiology of Urology journal.

## 7. DATA MANAGEMENT AND STATISTICAL ANALYSES

### 7.1 Data Management

Data forms will be completed for all subjects enrolled in the trial. The subject study files will be stored in a secure file cabinet and maintained by the research study coordinator. Subject study files will be kept for 7 years after the completion of the study. The final data will be entered into a database. The investigator will be responsible for management of the database. The database will be maintained within an organized and secure directory system.

Findings from this study will be submitted in abstract form to the annual meetings of the American Institute of Ultrasound in Medicine, the Radiological Society of North American, and the American Urological Association. A manuscript detailing study findings will also be submitted to either a Radiology of Urology journal.

### 7.2 Statistical Analyses

Qualitative findings will be generated from Radiologist interpretations of exams. Both 2D and 3D CEUS exams and the clinically-indicated contrast-enhanced MRI/CT exam will be independent and randomly

reviewed by two blinded radiologists with experience in both CEUS and body imaging. Readers will evaluate the presence of signal enhancement within the mass, signal distribution and heterogeneity, signal intensity relative to the normal renal parenchyma, and contrast agent wash-in and wash-out kinetics relative to the surrounding parenchyma. The readers will also be asked to evaluate if CEUS findings indicate RCC recurrence. This parameter will be based off of each reader's first read. In the event of discordant readings during this analysis, recurrence will be decided by consensus by the two readers. Finally, following a one month wait period and randomization, readers will again review cases in order to calculate intra-reader variability.

Quantitative findings will be generated by calculating of mass vascularity, perfusion, and contrast fill time. This will be done using a commercial contrast quantification package, which fits wash-in and wash-out curves to signal intensity as a function of time to quantify key parameters. Contrast parameters in the area of the previously treated mass will be computed relative to the surrounding renal parenchyma and again correlated to the clinical standard. Finally, the patient's billed amount for their contrast-enhanced MRI/CT exam (cost of exam prior to insurance reimbursements) will be recorded and compared to the cost of a real ultrasound exam and one vial of ultrasound contrast agent to compare potential cost savings to the patient.

Data will first be analyzed on a per case basis (treating each case as an independent data point). However, analysis may also be performed on a patient by patient basis if a large number of enrolled patients undergo serial imaging (potentially required to ensure adequate enrollment). Sensitivity, specificity, accuracy, positive predictive value, and negative predictive value will be calculated for the qualitative data using both the standard of care contrast-enhanced CT or MRI, and pathology (if retreated) as the reference standard. The dichotomous parameter needed for these calculations will be derived by ascertaining whether blinded radiologists would recommend further treatment or not based on the degree of residual blood flow observed during the contrast-enhanced ultrasound. Correlations between these findings and both contrast-enhanced MRI or CT findings will be compared using the Fisher exact test. Inter-rater variability will be calculated using each reader's first set of reads, while intra-rater variability will be calculated by comparing each reader's initial and 1 month analysis. Intra-rater and inter-rater variability will be calculated using a Shrout and Fleiss Interclass Correlation [Shrout and Fleiss 1979]. Quantitative parameters will be compared between groups using a Student's t-test.

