### 7.2.1 Sample Size Calculation

We hope to enroll up to 100 patients within 22 months as part of this study. This should be achievable,

given that our Urology clinic sees approximately 200 cryoablation follow up patients annually. As this is a pilot feasibility study it is difficult to estimate statistical power *a priori*. However, a power analysis was run in PASS12 (NCSS LLC, Kaysville, UT) to estimate the size of the confidence interval when estimating the test's overall level of specificity. A two sided confidence interval of one proportion was simulated using a Clopper-Pearson exact solution, assuming 100 patients and a total study recurrence rate of 5%. The relationship between the confidence level and 95% confidence interval and confidence interval width is shown below.

Confidence Level	Size (N)	Target Width	Actual Width	Proportion (P)	Lower Limit	Upper Limit	Width if P = 0.5
0.800	95		0.089	0.900	0.849	0.938	0.141
0.850	95		0.099	0.900	0.842	0.941	0.157
0.900	95		0.112	0.900	0.834	0.946	0.177
0.950	95		0.131	0.900	0.821	0.952	0.209

Thus, we expect 100 patients will enable us to estimate the specificity of the test to within 11% with 90% confidence. While multiple time points of the same patients cannot strictly be treated as independent samples (required to achieve adequate sample size within the two year window), data will also be analyzed on a per patient basis. Additionally, data from this study will also be used for future grant submissions to run a fully powered study in which conclusive hypotheses comparing 2D and 3D, as well as quantifiable parameters can be answered.

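### Section 7.2 leads with exams treated as independent, Section 7.2.1 says repeat exams are not; the per-patient analysis has no fixed rule and the unit of the 100 is unclear

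*Combined protocol and SAP*

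**What the plan says.** Section 7.2 sets the order of analysis: "Data will first be analyzed on a per case basis (treating each case as an independent data point". The contrast with a patient-level analysis in the next sentence shows that a case is an exam. That patient-level analysis is optional: "analysis may also be performed on a patient by patient basis if a large number of enrolled patients undergo serial imaging". How many is large is not stated. Serial imaging is described there as "potentially required to ensure adequate enrollment".

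Section 7.2.1 takes a different line. It opens the relevant sentence with "While multiple time points of the same patients cannot strictly be treated as independent samples", adds in parentheses "required to achieve adequate sample size within the two year window", and ends with "data will also be analyzed on a per patient basis". Neither section says which exam represents a patient or how several exams are combined.

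The Synopsis and Sections 4 and 7.2.1 word the 100 as adults or patients, and Section 4.2 numbers subjects 01 to 100. Section 3 lets a patient re-enroll at later follow-ups, with no rule on whether a new number is issued. Section 3.1 expects most patients to have one exam. Section 7.2.1 gives the precision target: "we expect 100 patients will enable us to estimate the specificity of the test to within 11% with 90% confidence".

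**The concern.** The plan leads with an assumption that its next subsection says does not strictly hold. The same ablation cavity, body habitus and acoustic window recur at each visit, so a false-positive read in one patient can repeat. Any interval for specificity or accuracy computed as if exams were independent can then be too narrow. The Fisher and t-tests in Section 7.2 rest on the same assumption.

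Because the per-patient analysis is optional in one section, promised in the other and undefined in both, its form could be settled after results are known. Precision for specificity is the only quantified support for the sample size, and Section 7.2.1 says the data will feed grant submissions for a fully powered study. An overstated precision would carry forward.

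**Working it through.** **1. The plan's own figure.** Inputs from Section 7.2.1: 100 patients, 5% recurrence, so 95 recurrence-free; specificity 0.90; two-sided Clopper-Pearson. With x = 0.9 × 95 = 85.5 and n = 95, the limits are the α/2 quantile of Beta(x, n−x+1) and the 1−α/2 quantile of Beta(x+1, n−x). Widths at 80/85/90/95% confidence are 0.0893, 0.0990, 0.1115 and 0.1308, matching the table. The 90% limits are 0.834 and 0.946, which lie 6.6 points below and 4.6 points above 0.90. The quoted 11% is therefore the full width.

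**2. Bounds on repeats.** Visits are at 8, 12, 18, 24 and 36 months (Section 4.1) and recruitment lasts 22 months (Section 3.1). Months 8 to 24 span 16 months, so four exams fit. Months 8 to 36 span 28 and 12 to 36 span 24, which do not. The maximum is four exams per patient.

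**3. Repeats fill the 100.** The documents give neither the distribution of exams nor the ICC, so both are assumed. With m exams per patient, design effect = 1 + (Σm²/Σm − 1) × ICC, and effective N = exams / design effect. Example, 40 patients with one exam, 20 with two and 5 with three: Σm = 95, Σm² = 40 + 80 + 45 = 165, ratio 1.737. At ICC 0.5 the design effect is 1 + 0.737 × 0.5 = 1.368 and effective N is 95/1.368 = 69.4. Naive coverage is that of the nominal 90% exact interval that ignores clustering (beta-binomial simulation, 40,000 runs). With independent exams it is 94%, because the exact interval is conservative.

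| 95 recurrence-free exams from | ICC | Effective N | 90% width | Naive coverage |
|---|---|---|---|---|
| 80 patients (65/15 with 1/2 exams) | 0.3, 0.5, 0.7 | 86.8, 82.0, 77.8 | 0.117, 0.121, 0.124 | 93%, 92%, 91% |
| 65 patients (40/20/5) | 0.3, 0.5, 0.7 | 77.8, 69.4, 62.7 | 0.124, 0.132, 0.140 | 91%, 89%, 87% |
| 60 patients (40/9/7/4) | 0.3, 0.5, 0.7 | 70.8, 60.6, 52.9 | 0.131, 0.143, 0.154 | 90%, 87%, 84% |

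At ICC 0.1 to 0.2 naive coverage is at least about 91% in all three patterns.

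**4. The 100 are distinct patients with extra exams.** If 95 recurrence-free patients give 113 exams (77/18), the naive width is 0.1015 against 0.107 to 0.113, and coverage is 93% to 91% at ICC 0.3 to 0.7. If they give 152 exams (63/14/11/7), the naive width is 0.087 against 0.102 to 0.120, and coverage is about 87% to 81–82%. In this last pattern it is already 0.889 at ICC 0.2.

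**5. Tests.** Over the three patterns in step 3, with five recurrent patients giving one recurrent exam each, the nominal 5% t-test has error 5.1% to 5.8%. It reaches 6.5% to 8.8% only if one of four recurrent patients contributes two recurrent exams. Fisher stays at 1.9% to 4.2%.

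**6. Remedies compared.** At specificity 0.90 over the three patterns, nominal 95% coverage is 0.906 to 0.969 for the naive exact interval, about 0.935 to 0.955 for a patient-clustered robust interval on the logit scale, and 0.907 to 0.938 for a percentile patient bootstrap. In the 152-exam pattern at ICC 0.7 the bootstrap (0.916) beats the naive interval (0.899).

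**The case against.** Much of this is disclosed. Section 7.2.1 admits the dependence and promises a per-patient analysis, and *first* in Section 7.2 is an order, not a designation as primary. The study is a pilot. Section 7.2 specifies no confidence intervals for the results, so an interval that is too narrow is a risk only if one is reported. With few repeats, which Section 3.1 expects, or with a low ICC, the naive exact interval still covers at or above 90% when repeats fill the 100. All of that stands and limits the severity. It does not remove the conflict between the two sections, the missing exam rule, or the independence behind the only precision figure.

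Four stronger readings are tempting, and the documents do not support them:

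- That the table is miscalculated. It reproduces exactly.
- That per-exam specificity is itself biased. Clustering affects its precision; nothing here challenges the point estimate.
- That the 100 must count exams. Every explicit statement says adults, patients or subjects. The clinic sees about 200 follow-up patients a year, or 200 × 22/12 ≈ 367 over the recruitment period if they are not the same people, so 100 distinct patients may be attainable. The parenthetical remarks only suggest that exams may count.
- That the Fisher and t-test p-values are seriously wrong. Their error is little affected unless a recurrent patient is imaged more than once while recurrent.

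**Conclusion.** Wrong as written; minor to moderate in this pilot. The contradiction on independence, the conditional versus unconditional per-patient analysis, and the absent exam rule are plain from Sections 7.2 and 7.2.1 and need no assumption. The size does: it rests on assumed exam patterns, ICC 0.3 to 0.7 and specificity 0.90. On those assumptions the effect is negligible at about 1.2 exams per patient (95/80). It is moderate at about 1.6 (95/60), where the full 90% width is 0.131 to 0.154 rather than 0.112. The problem does not vanish if the 100 are distinct patients, because heavy repeat imaging would then make the naive interval narrower than the data justify.

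**What to change.** 1. **Section 7.2, all-exam analysis.** Define a case as one exam, delete the statement that each case is an independent data point, and say that any interval reported for an all-exam measure is clustered by patient. A GEE or robust interval on the logit scale is preferred; a patient-level bootstrap need not be ruled out.
2. **Both sections, per-patient analysis.** Make it unconditional, with a rule set without reference to the CEUS read. For specificity use each patient's first reference-negative exam, and for sensitivity each patient's first reference-positive exam, with exact intervals. A patient who recurs later then keeps the earlier recurrence-free exam. For the Fisher test and t-test use one exam per patient: the first reference-positive exam if there is one, otherwise the first eligible exam. State that recurrent exams may then come from later visits, so time since ablation is partly mixed with disease status.
3. **Section 7.2.1.** State whether the 100 counts patients or exams. Describe 0.112 (0.834 to 0.946) as the full 90% width for 95 independent units at specificity 0.90. Note that it widens if repeat exams fill the 100: 0.122, 0.137 and 0.143 with one exam from each of 80, 65 and 60 recurrence-free patients.

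The cost is plan wording, slightly more analysis code, and a slightly less favourable stated precision if repeats are common. No added patients or procedures are needed.

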### 7.2.1 Sample Size Calculation

We hope to enroll up to 100 patients within 22 months as part of this study. This should be achievable,

given that our Urology clinic sees approximately 200 cryoablation follow up patients annually. As this is a pilot feasibility study it is difficult to estimate statistical power *a priori*. However, a power analysis was run in PASS12 (NCSS LLC, Kaysville, UT) to estimate the size of the confidence interval when estimating the test's overall level of specificity. A two sided confidence interval of one proportion was simulated using a Clopper-Pearson exact solution, assuming 100 patients and a total study recurrence rate of 5%. The relationship between the confidence level and 95% confidence interval and confidence interval width is shown below.

Confidence Level	Size (N)	Target Width	Actual Width	Proportion (P)	Lower Limit	Upper Limit	Width if P = 0.5
0.800	95		0.089	0.900	0.849	0.938	0.141
0.850	95		0.099	0.900	0.842	0.941	0.157
0.900	95		0.112	0.900	0.834	0.946	0.177
0.950	95		0.131	0.900	0.821	0.952	0.209

Thus, we expect 100 patients will enable us to estimate the specificity of the test to within 11% with 90% confidence. While multiple time points of the same patients cannot strictly be treated as independent samples (required to achieve adequate sample size within the two year window), data will also be analyzed on a per patient basis. Additionally, data from this study will also be used for future grant submissions to run a fully powered study in which conclusive hypotheses comparing 2D and 3D, as well as quantifiable parameters can be answered.

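### The sample-size conclusion gives the full width of the 90% interval for specificity as if it were a margin of error

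*Combined protocol and SAP*

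**What the plan says.** All the relevant text is in section 7.2.1 (Sample Size Calculation) of the combined protocol and SAP.

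- **Enrolment.** It is framed as a ceiling: "We hope to enroll up to 100 patients within 22 months as part of this study". The section calls the study a pilot for which power is hard to state in advance, and offers a precision calculation instead.
- **Purpose.** The calculation was run "to estimate the size of the confidence interval when estimating the test's overall level of specificity".
- **Method.** "A two sided confidence interval of one proportion was simulated using a Clopper-Pearson exact solution". The inputs are an enrolment of 100 with recurrence in 5% of cases. This leaves 95 recurrence-free cases as the denominator for specificity, and the table uses N = 95.
- **Introduction to the table.** "The relationship between the confidence level and 95% confidence interval and confidence interval width is shown below".
- **Table.** There are four rows, at confidence levels 0.80, 0.85, 0.90 and 0.95. From the Actual Width column onward, the 90% row reads "0.112 0.900 0.834 0.946 0.177" and the 95% row "0.131 0.900 0.821 0.952 0.209". The five entries are the width, the assumed proportion, the lower limit, the upper limit, and the width if the proportion were 0.5.
- **Conclusion.** 100 patients are expected to let the team "estimate the specificity of the test to within 11% with 90% confidence".

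**The concern.** To estimate a quantity to within some distance ordinarily means that the estimate lies no further than that distance from the truth, on either side. Read that way, the conclusion promises plus or minus 11 points. The 11% is instead the distance between the two ends of the interval, so the error bar in the text is not the one the table supports.

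Two things make this worth correcting. First, the precision calculation is the only statistical support for the figure of 100, and this sentence is its conclusion. Taken literally, it does not explain the sample size, because a margin of 11 points would be reached with far fewer than 95 recurrence-free cases. Second, the section says that data from this pilot will support applications for a fully powered study, so a summary sentence of this kind may be lifted without the table beside it.

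The sentence introducing the table is a smaller, related slip. It speaks of a 95% interval, but only the last row is one, and the conclusion rests on the 90% row.

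**Working it through.** **Inputs, all from section 7.2.1.** 100 patients; recurrence rate 5%, so n = 100 × 0.95 = 95; assumed specificity 0.90, so x = 0.90 × 95 = 85.5; two-sided Clopper-Pearson interval.

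**Formula.** With α = 1 − confidence level:

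- lower limit = α/2 quantile of Beta(x, n − x + 1) = Beta(85.5, 10.5)
- upper limit = 1 − α/2 quantile of Beta(x + 1, n − x) = Beta(86.5, 9.5)

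**Step 1: reproduce the table.**

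| Level | Lower | Upper | Width | Width in plan | Width at P = 0.5 | P = 0.5 in plan |
|---|---|---|---|---|---|---|
| 80% | 0.8485 | 0.9378 | 0.0893 | 0.089 | 0.1409 | 0.141 |
| 85% | 0.8424 | 0.9413 | 0.0990 | 0.099 | 0.1568 | 0.157 |
| 90% | 0.8342 | 0.9457 | 0.1115 | 0.112 | 0.1774 | 0.177 |
| 95% | 0.8213 | 0.9521 | 0.1308 | 0.131 | 0.2088 | 0.209 |

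Every row agrees to within 0.001.

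**Step 2: identify the 11%.** In the 90% row, 0.946 − 0.834 = 0.112. The 11% is the full width.

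**Step 3: find the margins from the plan's own limits.**

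| Level | Below 0.90 | Above 0.90 | Half-width |
|---|---|---|---|
| 90% | 0.900 − 0.834 = 0.066 | 0.946 − 0.900 = 0.046 | 0.112 / 2 = 0.056 |
| 95% | 0.900 − 0.821 = 0.079 | 0.952 − 0.900 = 0.052 | 0.131 / 2 = 0.0655 |

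At 90%, 11.2 points is 11.2 / 5.6 = 2.0 times the half-width, 11.2 / 6.6 = 1.7 times the lower distance and 11.2 / 4.6 = 2.4 times the upper distance.

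**Step 4: look for any reading that gives an 11-point margin.**

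- The count 85.5 is not a whole number. At 90%, x = 85 gives width 0.114 (6.7 points below 85/95, 4.7 above), and x = 86 gives width 0.109 (6.5 below 86/95, 4.4 above).
- N = 100 in place of 95 gives width 0.108 at 90%; a Wald interval with N = 95 gives 0.101.
- At P = 0.5, the widest case, the 90% margin is 0.177 / 2, about 8.9 points. Even the 95% margin is 0.209 / 2, about 10.4 points.

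None of these gives a margin of 11 points.

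**Step 5: what an 11.2-point margin would require.** Keep specificity at 0.90, confidence at 90% and x = 0.9n, and search for the smallest n. The half-width falls to 0.112 or less at n = 27 (limits 0.751 to 0.975). The larger one-sided distance does so at n = 42 (limits 0.789 to 0.964). Both are well short of 95.

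**The case against.** The strongest defence is that context settles the meaning. The section says the aim was to find the size of the interval, the column is headed as a width, and the limits 0.834 and 0.946 stand just above the sentence. If the phrase is taken to mean an interval 11 points wide, it is correct, and it is correctly paired with the 90% row. The error is also conservative, because read as a margin it undersells the design. No sample size, analysis or conduct depends on it, in a declared pilot whose 100 patients are an upper limit. All of this stands as a limit on the point's importance. It does not rescue the sentence, whose usual meaning contradicts the limits beside it and which may be quoted without them.

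A reader might infer several stronger things that the documents do not support:

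- **That the calculation is wrong.** All four rows reproduce.
- **That the trial's only precision figure is faulty.** The table gives limits and widths at four levels, including 0.821 to 0.952 at 95%.
- **That the stray 95% corrupts the conclusion.** The introductory sentence also mentions a varying confidence level, the first column shows it, and the conclusion names 90% explicitly.
- **That the quoted level conflicts with the level at which results will be reported.** Sections 6.5 and 7.2 list sensitivity, specificity and the other measures without giving a level, so there is nothing to conflict with.

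**Conclusion.** The concluding sentence of section 7.2.1 misdescribes a correct number. At 90% confidence, with 95 cases and specificity of 0.90, the interval runs from 0.834 to 0.946: 6.6 points below, 4.6 above, half-width 5.6, full width 11.2. The text gives the full width as the margin, about twice the half-width. The direction is conservative and the planned sample size is unaffected. This is a correction of wording, worth making because the sentence is the stated conclusion of the trial's only statistical argument for 100 patients.

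The figures rest on the plan's own assumptions: exactly 5% recurrence, an observed specificity of about 0.90, and 95 independent recurrence-free cases. The limits are approximate because no data set can yield 85.5 correct results. The section itself concedes that repeated exams of one patient are not strictly independent; that is a separate matter and is not quantified here.

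**What to change.** Replace the concluding sentence of section 7.2.1 with:

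> With 95 independent recurrence-free cases and an observed specificity of about 0.90, the exact 90% CI would run from about 0.834 to 0.946 (6.6 points below, 4.6 above; full width 11.2 points), and the exact 95% CI from about 0.821 to 0.952 (7.9 below, 5.2 above; full width 13.1 points).

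In the sentence introducing the table, strike the reference to a 95% confidence interval, so that it describes only how interval width varies with confidence level.

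Naming the confidence level at which specificity will be reported would be a useful addition, but it is optional and not needed to correct this point.

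The cost is two sentences, using limits already in the table. Sample size, procedures and analysis stay as they are.
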